5.1.9. Unscheduled Visit

Any visits or procedures performed beyond those specified within the protocol must be documented in the Unscheduled Visit pages of the eCRF. Unscheduled visits may include but are not limited to reporting adverse events (AEs), changes in concomitant medications, or ophthalmic assessments as deemed appropriate by an appropriately qualified physician. If the subject is discontinuing study participation at the unscheduled visit, the Early Termination eCRFs should be completed rather than the Unscheduled Visit eCRFs.

5.1.10. Early Termination Visit

In the event of study termination prior to Visit 6 but following Visit 2, every attempt will be made to ensure that the following will be performed/assessed (when obtainable) (**NOTE:** All ocular assessments must be performed in both eyes.):

- Review use of any concomitant medications since the last visit
- Assess occurrence of any AEs since the last visit
- Collect used and unused investigational product and dosing diary
- Perform (when obtainable):

- Visual acuity assessed using the same method used at the screening visit
- Signs of anterior ocular inflammation – cell and flare grading, corneal clarity, conjunctival injection, chemosis, hypopyon as well as and vitritis and wound integrity assessed using the same method used at the screening visit
- Symptom assessment of anterior ocular inflammation – photophobia and lacrimation
- IOP measurement
- Dilated ophthalmoscopy
- Modified Global Overall Assessment of Postoperative Inflammation

5.2. SUBJECT WITHDRAWAL AND/OR DISCONTINUATION

Any parent/guardian who wishes to discontinue their child's investigational product use or withdraw their child from participation in the study for any reason is entitled to do so without obligation. The Investigator may also discontinue any subject from investigational product use or from study participation, if deemed necessary.

Investigational product use may be discontinued, and any subject may be discontinued from study participation at any time during the study at the discretion of the Investigator or the sponsor for any reason including but not limited to:

1. Occurrence of any medical condition or circumstance that exposes the subject to substantial risk and/or does not allow the subject to adhere to the requirements of the protocol.
2. Any SAE, clinically significant AE, severe, intercurrent illness, or other medical condition that indicates to the Investigator that continued participation is not in the best interest of the subject.
3. Parent's/guardian's decision to withdraw.
4. Parent's/caregiver's failure to comply with protocol requirements or study related procedures.
5. Termination of the study by the Sponsor, FDA, or other regulatory authorities.

In the event study discontinuation of a randomized subject is necessary, the Investigator should make every attempt possible to have the subject complete the Early Termination assessments. The Investigator should make every attempt to follow all serious adverse events (SAEs) to resolution. The reason for premature discontinuation should be recorded in the subject's chart.

Subjects who withdraw from the trial will not be replaced.

Additionally, the trial or parts of the trial may be discontinued by the sponsor or at the recommendation of the Investigator after consultation with Kala Pharmaceuticals, Inc. This may be based on a significant number of AEs of a similar nature that warrant such action.

5.3. COLLECTION OF DATA

Source documentation for data collected in this study will be maintained at the investigative site. The CRF will be electronic (eCRF) and data will be electronically entered from the source documentation into the eCRF. After study completion, an archival copy [e.g., portable document format (PDF)] of the eCRF data will be retained by the site.

5.4. RESCUE MEDICATION USE

Any subjects not responding adequately to the investigational product may be rescued and placed on alternate therapy at the Investigator's discretion at any time. The choice of rescue medication is at the Investigator's discretion. Any subject placed on rescue therapy will discontinue use of the investigational product and continue study participation through Visit 6.

Rescued subjects will be considered treatment failures, and the need for rescue therapy will not be considered an AE. Rescued subjects should not be withdrawn from the study, but rather followed through the end of the study/Visit 6.

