3. TRIAL DESIGN**3.1. PRIMARY EFFICACY EVALUATION**

The primary efficacy evaluation is the proportion of study eyes with anterior chamber cell grade = 0 at Visit 4 (Day 15 ± 2 days) without receiving rescue medication prior to Visit 4 as compared between the KPI-121 1% dosed BID and the prednisolone acetate 1% dosed QID treatment arms.

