6.2.2. Medications Not Permitted

Use of the following medications is not allowed during the study and for the timeframes specified:

Within 30 days prior to surgery and for the duration of the study:

- Other investigational products.

Within 14 days prior to surgery and for the duration of the study:

- The use of systemic, inhaled or ocular corticosteroids with the exception of intraoperative ocular corticosteroids.

Within 2 days prior to surgery and for the duration of the study:

- The use of any topical ophthalmic medication in the study eye, except for drops that are needed to examine the eye or to prepare for and undergo surgery, including post-operative antibiotic drops. **NOTE:** besifloxacin ophthalmic suspension is not permitted.
- The use of systemic or ocular non-steroidal anti-inflammatory drugs.
- Change in use of nutraceuticals or multivitamins.

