Modified Global Overall Assessment of Postoperative Inflammation

Based on the signs and symptoms scoring above the following overall categorization of inflammation will be assessed:

- 0 Clear
- 1 Improving satisfactorily
- 2 Not improving or worsening; allow rescue therapy

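### A child who switches to another anti-inflammatory before Visit 4 for a reason other than inadequate response can be counted as a success of the stopped product

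*Combined protocol and SAP*

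**What the plan says.** Section 3.1 makes the primary outcome a cell grade of 0 at Visit 4, "without receiving rescue medication prior to Visit 4". Section 3.2 sets the same condition for a global score of 0, and Section 9.1.2 carries both outcomes into the analysis.

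Rescue is described in two places, each time by lack of response. Section 5.4: "Any subjects not responding adequately to the investigational product may be rescued and placed on alternate therapy". The global scale in Section 9.1.2 and Appendix 6 labels its worst category "Not improving or worsening; allow rescue therapy". The consequence is in Section 5.4: "Rescued subjects will be considered treatment failures, and the need for rescue therapy will not be considered an AE". The synopsis and Section 9.1.2 also apply the term treatment failure to rescued subjects and to no one else.

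Section 5.2 treats stopping product and leaving the study as separate events: "The Investigator may also discontinue any subject from investigational product use or from study participation, if deemed necessary". Its list of reasons includes "Any SAE, clinically significant AE, severe, intercurrent illness, or other medical condition that indicates to the Investigator that continued participation is not in the" child's best interest. It attaches no outcome rule to either event.

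Section 6.2.2 prohibits, for the duration of the study, "The use of systemic, inhaled or ocular corticosteroids with the exception of intraoperative ocular corticosteroids". It also prohibits systemic and ocular NSAIDs. It does not say that using one makes the subject a failure.

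**The concern.** The plan already takes the view that a grade of 0 reached on rescue treatment should not be credited to the assigned product. The same reasoning applies to a child who stops product for, say, an adverse event and clears on a different anti-inflammatory. As written, however, that child falls outside the description of rescue and can satisfy every element of the success definition.

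Two things are at stake. The first is the success percentage itself. All efficacy analysis is descriptive (Sections 9.1.2 and 9.3), so these percentages are the efficacy result, and no planned test or margin stands beside them. The second is consistency. Section 5.4 leaves the choice of rescue drug to the investigator, so the same drug could be recorded as rescue at one of the roughly 20 centers and as a concomitant medication at another. The outcome would then depend on a site's label.

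**Working it through.** **1. Following one child through the rules.** Suppose a child stops product on Day 8 for an adverse event, starts a non-study ocular corticosteroid, stays in the study and has cell grade 0 at Visit 4.

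- *Endpoint (3.1, 3.2):* the grade is 0. Whether the child received rescue medication depends on the label. By the description in 5.4 the answer is no, because the trigger was not inadequate response.
- *Recording (6.2):* indication, dates, route and whether the drug was taken for an AE are captured for each medication, while 5.4 says that needing rescue is not itself an AE. A switch for an AE therefore fits most naturally as a concomitant medication.
- *ITT (9.6):* randomized with a post-randomization assessment, so included, and counted as a success if not labelled rescued.
- *Per Protocol (9.1.2, 9.6):* requires 15 ± 2 days of product use and no significant deviations. The child would normally be dropped. Only rescued subjects are expressly kept in, as failures.
- *Tipping-point rule (9.4):* triggered by missing Day 15 data. This child's Day 15 value is observed, so the rule does not reach it.

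No planned analysis turns this child's ITT success into a failure.

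**2. The plan's own figure.** Section 9.2 gives 30 per group for at least a 95% chance of seeing an AE with 10% incidence. The formula is 1 − 0.9^n: n = 28 gives 0.948, n = 29 gives 0.953, n = 30 gives 0.958. The stated 30 meets the requirement (the smallest n is 29) and is not in dispute. It serves below as the denominator.

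**3. Effect per child.** Shift in an arm's success percentage = 100 × k/30.

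| Children reclassified (k) | Shift in that arm |
|---|---|
| 1 | 3.3 points |
| 2 | 6.7 points |
| 3 | 10.0 points |

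For example, 18/30 = 60.0% becomes 17/30 = 56.7% with one child reclassified.

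**4. Expected effect under assumed rates.** The documents give no switch rate. Assume that 3% to 10% of an arm switches before Visit 4 for a reason other than inadequate response, and that 30% to 70% of those are at grade 0 at Visit 4.

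- Expected overstatement in one arm = switch rate × share at grade 0. Low: 0.03 × 0.30 = 0.9 points. High: 0.10 × 0.70 = 7.0 points.
- Chance of at least one such child among 30 = 1 − (1 − rate × share)^30. Low: 1 − 0.991^30 = 24%. High: 1 − 0.93^30 = 89%.
- If the arms switch at 10% and 3% with the same share at grade 0, the between-arm difference shifts by (0.10 − 0.03) × 0.30 = 2.1 points to (0.10 − 0.03) × 0.70 = 4.9 points.
- If the rates are equal and the share is the same, the expected shift in the difference is zero, although both percentages are overstated.

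**The case against.** The strongest objection is that the endpoint excludes eyes that received rescue medication without stating a reason. Section 5.4 says who may be rescued; it does not define rescue medication as a drug given only for lack of efficacy. A site could record any alternate anti-inflammatory as rescue, and the child would then be a failure. This stands. A reader might infer that the protocol contains a rule that forces a wrong classification, or that rescue is the only route to non-success. The documents support neither: the term is undefined, and a grade above 0 at Visit 4 is also a non-success.

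The AE item in Section 5.2 speaks of continued participation, which points toward leaving the study. Retention through Visit 6 is expressly required only for rescued subjects. A child who leaves before Visit 4 has missing data, which the tipping-point rule may cover. This narrows the route but does not close it, because the same section names stopping product alone.

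A non-rescue switch to a prohibited drug is a protocol deviation, the Per Protocol set offers a comparison, and AEs are tabulated by arm. These are partial safeguards: the tolerability problem would be visible, but the ITT percentage would be unchanged.

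Using the observed grade after a switch is a recognised treatment-policy approach. That is true, but the plan has already chosen a composite approach for rescue and does not say that it intends a different one for other switches.

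A reader might also infer that switching for raised IOP would hide the failures of one product. The documents exclude children with raised IOP at entry and measure IOP as a safety outcome. They do not say that a rise leads to a switch to another anti-inflammatory, or that the arms would differ. That mechanism is conjecture.

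**Conclusion.** The concern holds as a gap that permits misclassification in the ITT primary and secondary outcomes. It applies only when all of these are true: product is stopped for a reason other than inadequate response, another anti-inflammatory starts before Visit 4, the child stays in the study, the site does not label the event rescue, and the Visit 4 grade (or score) is 0.

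The arithmetic fact is 3.3 points per child in an arm of 30. Everything beyond that rests on assumption. Under the ranges used, the expected overstatement is 0.9 to 7.0 points in an arm, and the difference shifts by 2.1 to 4.9 points if the arms switch at 10% and 3%. One to three such children in a single arm and none in the other would shift the difference by 3.3 to 10.0 points, but that is a one-sided extreme. With no test or margin planned, no formal decision can reverse; what changes is the reported percentages and the reading of them.

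Section 9.5 mentions a statistical analysis plan, but the document holds no separate SAP text. A rule written there would settle the point.

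**What to change.** In Sections 3.1, 3.2 and 9.1.2, count as non-success any eye whose subject started, after randomization and before the Visit 4 assessment, a non-study corticosteroid or NSAID in the study eye, or a systemic corticosteroid. The rule applies for any reason and whether or not the site labelled the drug rescue. Report the version based on the site's rescue label, with the observed Visit 4 grade, as a sensitivity analysis.

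State also how the analysis treats cases that this rule leaves out: product stopped with no replacement, and the inhaled corticosteroids and systemic NSAIDs that Section 6.2.2 also prohibits. The rule keeps the timing of Section 3.1 (before Visit 4). Section 9.1.2 words the primary condition as running through Visit 4; that is a separate inconsistency to reconcile on its own.

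The cost is endpoint wording and one derivation. Section 6.2 already collects drug, route, dates, indication and the AE flag, so no new data are needed, and care, visits and sample size do not change. The downside is that a few eyes that would have cleared anyway count as failures; the sensitivity analysis shows how much that matters.

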6. TREATMENT OF SUBJECTS**6.1. INVESTIGATIONAL PRODUCTS TO BE ADMINISTERED**

KPI-121 1% and vehicle or prednisolone acetate 1% will be supplied as investigational product. One Kit of randomized investigational product containing four dropper bottles will be allocated to each subject at Visit 2.

The investigational product will be stored at the site upright in a secure area, with limited access, at 15-25°C/59-77°F.

Parents/caregivers will be asked to administer investigational product four times daily during the treatment phase. Instillation of the four doses should be spaced throughout the day at the approximate time points of: morning (Bottle 1), midday (Bottle 2), afternoon (Bottle 3), and bedtime (Bottle 4). Prior to each instillation of investigational product, the parent/caregiver will be instructed to shake the investigational product bottle well. The parent/caregiver will record the time of administration and number of drops administered for each dose of investigational product in the Daily Dosing Diary ([Appendix 7](#)).

Additional investigational product will be dispensed at Visit 4 and discontinued at Visit 5. Used investigational product kits will be collected by the study staff at Visits 4 and 5.

Compliance with instillation of investigational product will be assessed at each clinic visit and reviewed with the parent/caregiver if poor compliance is noted.

6.2. CONCOMITANT MEDICATIONS

With the exception of peri-operative standard of care medications, all medication that the subject has taken 30 days prior to Visit 1 and through Visit 6 or discontinuation from the study will be recorded in the subject's chart/source documents and the eCRF. The name of the drug, dose, route of administration, duration of treatment (including start and stop dates), frequency, indication, and whether or not the medication was taken due to an AE will be recorded for each medication.

6.2.1. Permitted Medications

Medications not specifically excluded in [Section 6.2.2](#) may be taken as necessary. Concomitant treatment with ocular antibiotics at the discretion of the Investigator is allowed (with the exception of besifloxacin). Medications routinely administered (and not explicitly prohibited in this protocol) as part of an uncomplicated cataract surgery

procedure are allowed. These medications will be collected in a summary source document and will not be captured within the eCRF. If there is a change from the standard of care as documented in the source document, the medication will be added to the eCRF. Further, the routine medications administered as part of routine cataract surgery are not expected to be associated with treatment for AEs unless otherwise indicated. **NOTE:** Any medication administered as part of the routine surgery that is ongoing subsequent to the surgical procedure should be captured in the eCRF as a concomitant medication.

6.2.2. Medications Not Permitted

Use of the following medications is not allowed during the study and for the timeframes specified:

Within 30 days prior to surgery and for the duration of the study:

- Other investigational products.

Within 14 days prior to surgery and for the duration of the study:

- The use of systemic, inhaled or ocular corticosteroids with the exception of intraoperative ocular corticosteroids.

Within 2 days prior to surgery and for the duration of the study:

- The use of any topical ophthalmic medication in the study eye, except for drops that are needed to examine the eye or to prepare for and undergo surgery, including post-operative antibiotic drops. **NOTE:** besifloxacin ophthalmic suspension is not permitted.
- The use of systemic or ocular non-steroidal anti-inflammatory drugs.
- Change in use of nutraceuticals or multivitamins.

6.3. INVESTIGATIONAL PRODUCT USE COMPLIANCE

Compliance will be assessed using the dosing information recorded in the Daily Dosing Diary completed by the parent/caregiver.

6.4. DRUG ACCOUNTABILITY

The sponsor's study monitors or designees will conduct accountability of investigational product (KPI-121 1%, vehicle, and prednisolone acetate 1%). Accountability will be ascertained by performing reconciliation between the amount of investigational product sent to the site and the amount of used and unused investigational product at the time of reconciliation.

Investigational product will be shipped to the investigational sites under sealed conditions. Investigational product shipment records will be verified by comparing the shipment inventory sheet to the actual quantity of drug received (i.e., kit level accounting) at the site. Accurate records of receipt and disposition of the investigational product (e.g., dates, subject number, kit number dispensed, and kits and bottles returned) must be maintained by the Investigator or his/her designee. Investigational product will be stored upright in a secure area, with limited access, at 15-25°C/59-77°F.

At the end of the study, all investigational product (KPI-121 1%, vehicle and prednisolone acetate 1%), including all used and unused bottles and kits, will be returned to the drug packaging vendor in accordance with sponsor or designee's standard operating procedures (SOPs), following approval by the Sponsor. All returns of investigational product will be documented. The study monitor or designee will verify drug accountability. All drug accounting procedures must be completed before the study is considered complete.

6.5. MAINTENANCE OF RANDOMIZATION AND PROCEDURE FOR BREAKING THE CODE

The sponsor, the project teams at the designated Contract Research Organizations (CROs), and investigative staff responsible for assessments of study endpoints will be masked to investigational product assignments. In case of medical emergency, or occurrence of an SAE, the randomization code may be unmasked and made available to the Investigator, sponsor, and/or other personnel involved in the monitoring or conduct of this study. In the absence of medical need, the randomization code will not be available to the above individuals until after the study is completed and the database is locked.

In the event of a medical need, the Investigator will treat each subject as needed. Since there is no specific antidote to KPI-121 1%, immediate emergency unmasking is not necessary. If the Investigator feels it is necessary to unmask a subject's assignment after an emergency situation, the Investigator may call the medical monitor and notify the sponsor. The investigational product assignment will be revealed on a subject-by-subject basis with the approval of the medical monitor and sponsor, thus leaving the masking of the remaining subjects intact.

A randomization code for assignment of subjects to treatment arms will be computer-generated by Kala Pharmaceuticals, Inc. or its designee.

Randomization team members, specifically the designated dosing coordinator(s), will work independently of other team members at the site. Study personnel, study subjects, the sponsor, and project teams at the CROs involved in the study will be masked to investigational product assignments.

7. ASSESSMENT OF EFFICACY

7.1. EFFICACY PARAMETERS

Efficacy Assessments include the following:

- Signs of anterior ocular inflammation – cell and flare grading, corneal clarity, conjunctival injection, chemosis, hypopyon as well as vitritis and wound integrity
- Investigator assessment of symptoms of anterior ocular inflammation – photophobia and lacrimation
- Modified Global Overall Assessment of Postoperative Inflammation
- Use of rescue therapy

8. ASSESSMENT OF SAFETY

8.1. SAFETY PARAMETERS

Safety assessments include the following:

- Assessments of AEs
- Visual Acuity
- IOP Measurement
- Dilated Ophthalmoscopy

8.2. ADVERSE EVENT DEFINITIONS

Adverse Event (AE): Any untoward medical occurrence associated with the use of an investigational product in humans, whether or not considered drug related.

Adverse Reaction (AR): Any AE caused by a drug. Adverse reactions are a subset of all suspected adverse reactions where there is reason to conclude that the drug caused the event.

Suspected Adverse Reaction (SAR): Any AE for which there is a reasonable possibility that the drug caused the AE. For the purposes of IND safety reporting, “reasonable possibility” means there is evidence to suggest a causal relationship between the drug and the AE. A SAR implies a lesser degree of certainty about causality than adverse reaction, which means any AE caused by a drug.

Unexpected: An AE or SAR is considered “unexpected” if it is not listed in the Investigator’s Brochure or is not listed at the specificity or severity that has been observed.

Life-threatening: An AE or SAR is considered “life-threatening” if, in the view of either the Investigator or sponsor, its occurrence places the patient or subject at immediate risk of death. It does not include an AE or suspected adverse reaction that, had it occurred in a more severe form, might have caused death.

A **SERIOUS ADVERSE EVENT (SAE)** is any AE or suspected adverse reaction occurring at any dose that:

- Results in death.
- Is life-threatening.
- Results in a persistent or significant incapacity or substantial disruption of the ability to conduct normal life functions.
- Requires inpatient hospitalization.
- Prolongs inpatient hospitalization.
- Is a congenital anomaly/birth defect.
- Is a significant medical event (i.e., one that may jeopardize the subject or may require intervention to prevent one or more of the other outcomes listed above).

A **NON-SERIOUS ADVERSE EVENT** is any AE that does not meet the definitions for SAEs as described above.

Each **AE** will be classified as **SERIOUS** or **NON-SERIOUS** using the definitions provided above.

The **SEVERITY** of each AE will be classified as **MILD, MODERATE, or SEVERE**. The Investigator will review each event and assess its **RELATIONSHIP** to use of investigational product (unrelated, unlikely, possibly, probably, definitely). The AE will be assessed using the following definitions:

Unrelated:

- Event or intercurrent illness due wholly to factors other than investigational product use.

Unlikely:

- Poor temporal relationship with investigational product use.
- Event easily explained by subject's clinical state or other factors.

Possible:

- Reasonable temporal relationship with investigational product use.
- Event could be explained by subject's clinical state or other factors.

Probable:

- Reasonable temporal relationship with investigational product use.

- Likely to be known reaction to agent or chemical group or predicted by known pharmacology.
- Event cannot easily be explained by subject's clinical state or other factors.

Definitely:

- Distinct temporal relationship with investigational product use.
- Known reaction to agent or chemical group, or predicted by known pharmacology.
- Event cannot be explained by subject's clinical state or other factors.

(NOTE: Expected changes such as the presence of inflammation resulting from routine uncomplicated cataract surgery will not be captured as AEs.)

